7.1.7 Follow-up of adverse events

All AEs will be followed until they have abated, returned to baseline status or until a stable situation has been reached. Depending on the event, follow up may require additional tests or medical procedures as indicated, and/or referral to the general physician or a medical specialist.

7.1.8 Adverse events of special interest

An AESI (serious or non-serious) is one of scientific and medical concern for which ongoing monitoring and rapid communication by the investigator to the sponsor can be appropriate. Adverse events of special interest for this study include QTc prolongation as well as liver tests that meet the criteria for potential drug-induced liver injury (DILI), in accordance with the US Food and Drug Administration "Guidance for Industry-Drug-Induced Liver Injury: Premarketing Clinical Evaluation".

Adverse event of special interest: QTc prolongation

A thorough QT study (PM1116628) was conducted in healthy volunteers who received losmapimod at 7.5 mg BID or 20 mg daily or with placebo administered for 5 days. At the 20 mg dose of losmapimod, the upper bound of the 90% CI of the $\Delta\Delta QT$ interval (change from baseline in QTcF compared with that for placebo) exceeded the 10 msec threshold at the 24-hour post-dose time point. For the 7.5 mg BID dose, the upper bound of the 90% CI of $\Delta\Delta QTcF$ exceeded the 10 msec threshold at multiple time points. No subjects experienced QTcF values >480 msec or QTcF changes from baseline ≥ 60 msec at any time in the study. Although the upper bound of the 90% CI exceeded the 10 msec regulatory threshold of concern in the primary pharmacodynamic analysis, it was determined by GSK that there was no clinically relevant effect on the QT interval, as there was no clinically relevant concentration QTc effect using standard placebo/baseline subtracted measured QTc data. Additional information on the QTc interval and its behavior, as demonstrated in the large cohort of patients with ACS treated with losmapimod (PM1116197), supported the lack of a QT effect. PK/PD modeling using the raw QTcF and plasma concentration data showed that at plasma losmapimod concentrations 4 times the exposure at the therapeutic dose (7.5 mg BID) (ie, at exposures approximately 2-fold higher than 15 mg BID, the predicted upper bound of the 90% CI of $\Delta\Delta QTcF$) did not exceed 10 msec, and the predicted median $\Delta\Delta QTcF$ was less than 5 msec. Further details are presented in the [Investigator Brochure](#). No drug effect on QT prolongation of

Fulcrum Therapeutics
Protocol FIS-001-2020

Losmapimod

Losmapimod over placebo has been documented in any of the phase 2 or the one phase 3 trial completed so far.

Study drug should be discontinued for subjects who meet the QTc prolongation criteria as a result of within-protocol specific testing or unscheduled testing (see [Section 3.4.4](#) stopping criteria). This AESI must be reported to the sponsor within 24 hours of awareness per the SAE reporting procedures ([Section 7.1.6](#)). Further safety steps should be taken to closely observe and follow-up the event until resolution and treatment initiated per local standard of care.

Adverse event of special interest: Drug-induced liver injury

The following 3 laboratory value criteria must be met for potential DILI, or "Hy's Law":

- An elevated alanine transaminase or aspartate transaminase laboratory value that is $\geq 3 \times$ ULN
- An elevated total bilirubin laboratory value that is $\geq 2 \times$ ULN
- An alkaline phosphatase laboratory value that is $< 2 \times$ ULN

Study drug should be discontinued for subjects who meet the laboratory criteria for potential DILI as a result of within-protocol specific testing or unscheduled testing (see [Section 3.4.4](#) stopping criteria). This AESI must be reported to the sponsor within 24 hours of awareness per the SAE reporting procedures ([Section 7.1.6](#)). Further safety steps should be taken to closely observe and follow-up the event until resolution. These steps include, but are not limited to:

- Making every reasonable attempt to have the subject return to the clinic within 24 hours for repeat liver tests
- Obtaining a more detailed history of symptoms and prior or concurrent disease, concomitant medication use, alcohol use, recreational drug use, and special diets
- Repeating liver enzyme and serum bilirubin tests twice weekly. Frequency of retesting can decrease to once a week or less if abnormalities stabilize and the subject is asymptomatic
- Obtaining viral hepatitis serology
- Considering liver imaging and/or hepatology consultation

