Based on the current safety and exposure information, dosing adjustment is likely not needed for subjects with renal insufficiency. However, close monitoring of pharmacokinetics (PK) for such cases will be implemented to ensure that therapeutic concentrations are maintained (refer to **Section 6.2**). For those subjects requiring dialysis, dose adjustment may be needed and will be determined by pre- and post-dialysis PK by the DMC. Adjustments may be recommended by the DMC also for subjects on placebo who develop acute renal failure to prevent unblinding at the sites.

Study treatment discontinuation

Discontinuation of study treatment should be considered if:

- ALT or AST >8 x the upper limit of normal (ULN)
- ALT or AST >5 x ULN for more than 2 weeks
- ALT or AST >3 x ULN and (total bilirubin >2 x ULN or international normalized ratio >1.5) in the absence of reasonable alternative etiology
- ALT or AST >3 x ULN with the appearance of fatigue, nausea, vomiting, right upper quadrant pain or tenderness, fever, rash, and/or eosinophilia (>5%)
- QTcF prolongation with QTcF >500 msec or an increase in QTcF of >60 msec over baseline (confirmed by 2 successive repeat measurements)

In addition, the investigator must permanently discontinue the study drug if continued administration of the study drug is believed to be contrary to the best interests of the subject. The premature discontinuation of study drug might be triggered by an adverse event (AE), a diagnostic or therapeutic procedure, an abnormal assessment (eg, ECG or laboratory abnormalities), pregnancy, or for administrative reasons, in particular noncompliance with the protocol or withdrawal of the subject's consent. The reason for study drug interruption or premature discontinuation must be clearly documented in the eCRF.

Fulcrum Therapeutics
Protocol FIS-001-2020

Losmapimod

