3.4.4 Stopping criteria

Dosing will be stopped in case of an unacceptable tolerability profile based on the nature, frequency, and intensity of observed AEs judged jointly by the investigator and the sponsor or as recommended by the DMC.

In the event of a study hold due to unacceptable tolerability, the sponsor will conduct an extensive safety and PK analysis and will communicate to stakeholders, including the Investigators, institutional review boards (IRBs)/independent ethics committees (IEC), and health authorities any potentially emergent safety information as well as the timing of planned resumption of dosing. Dosing and enrollment will not resume unless it is considered safe to do so after consultation with Investigators and health authorities and approval by IRBs/IECs.

Fulcrum Therapeutics
Protocol FIS-001-2020

Losmapimod

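### Protocol Sections 3.4.1 and 7.1.8 give different study-drug instructions for QTc prolongation and potential liver injury, and 7.1.8 cites a section with no threshold for either

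*Protocol*

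**What the plan says.** Three sections of Protocol version 3.0 bear on this.

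**Section 3.4.1**, under the discontinuation subheading, opens with "Discontinuation of study treatment should be considered if" and lists four liver triggers and one QTc trigger. The liver trigger closest to Hy's Law is "ALT or AST >3 x ULN and (total bilirubin >2 x ULN or international normalized ratio >1.5) in the absence of reasonable alternative etiology". The QTc trigger is a QTcF above 500 msec, or a rise of more than 60 msec from baseline, confirmed by two repeats.

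**Section 7.1.8** covers the two named adverse events of special interest.
- QTc: "Study drug should be discontinued for subjects who meet the QTc prolongation criteria". The section sets no on-treatment criterion. Its QTcF figures are background results from an earlier thorough QT study.
- Liver: "The following 3 laboratory value criteria must be met for potential DILI". They are ALT or AST at least 3 x ULN, total bilirubin at least 2 x ULN and alkaline phosphatase below 2 x ULN. The action is "Study drug should be discontinued for subjects who meet the laboratory criteria for potential DILI".

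Each of these two actions refers the reader to Section 3.4.4 for the stopping criteria.

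**Section 3.4.4** is a trial-level rule: "Dosing will be stopped in case of an unacceptable tolerability profile based on the nature, frequency, and intensity of observed AEs". It gives no transaminase, bilirubin, alkaline phosphatase, INR or QTc value.

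**The concern.** These are working safety rules for individual subjects. A site that acts from 3.4.1 may keep a subject on drug whom 7.1.8 says to stop. A site that starts from 7.1.8 and follows its reference finds no threshold.

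Three features of the trial make this more than untidy wording.
- Section 3.4.1 does not allow doses to be interrupted or reduced (dialysis adjustment apart). A site cannot hold drug while it repeats tests, so the choice between considering and stopping decides whether dosing continues.
- Exclusion criterion 5 admits subjects with ALT or AST just under 5 x ULN and bilirubin up to 1.5 x ULN. A subject with normal alkaline phosphatase can enter already meeting two of the three liver criteria in 7.1.8, and needs only a rise in bilirubin to 2 x ULN to meet the third.
- Section 7.1.8 reports that in the thorough QT study the upper 90% confidence bound passed 10 msec at several time points at 7.5 mg twice daily. This trial gives 15 mg twice daily. The previous developer judged the finding not clinically relevant, but QTc was still made an event of special interest here.

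**Working it through.** The documents give no figure to reproduce. The check compares the rules as written and applies them to the same subject.

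| | Section 3.4.1 | Section 7.1.8 |
|---|---|---|
| QTc trigger | QTcF >500 msec or rise >60 msec, confirmed twice | none given; refers to 3.4.4 |
| QTc action | consider stopping | stop |
| Nearest liver trigger | ALT/AST >3 x ULN, with bilirubin >2 x ULN or INR >1.5 | ALT/AST >=3 x, bilirubin >=2 x and alkaline phosphatase <2 x ULN |
| Alternative-cause exception | yes | no |
| Liver action | consider stopping | stop |

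**QTc.** Since 7.1.8 sets no criterion, the only usable one is in 3.4.1. Take a QTcF of 510 msec confirmed by two repeats. 510 > 500, so the 3.4.1 trigger is met and stopping is to be considered. Under 7.1.8 the same subject is to be stopped. There is one threshold and two strengths of instruction.

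**Liver.** Take ALT 4 x ULN, bilirubin 2.5 x ULN, alkaline phosphatase 1.5 x ULN, a plausible alternative cause, none of the symptoms listed in 3.4.1 and eosinophils not above 5%.

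Section 3.4.1:
1. ALT/AST >8 x ULN: 4 is not above 8. Not met.
2. ALT/AST >5 x ULN for more than 2 weeks: 4 is not above 5. Not met.
3. ALT/AST >3 x with bilirubin >2 x or INR >1.5, no alternative cause: 4 > 3 and 2.5 > 2, but the cause clause fails. Not met.
4. ALT/AST >3 x with a listed symptom or eosinophilia: none present. Not met.

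Total: 0 of 4.

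Section 7.1.8:
1. 4 >= 3: met.
2. 2.5 >= 2: met.
3. 1.5 < 2: met.

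Total: 3 of 3, so stop.

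Varying the example:
- With one listed symptom added, 3.4.1 scores 1 of 4, and its instruction is still only to consider.
- With no alternative cause and no symptom, trigger 3 is met and 3.4.1 again says consider. Section 7.1.8 says stop.
- With alkaline phosphatase at 2.5 x ULN and no alternative cause, 3.4.1 says consider and 7.1.8 does not apply. There is no conflict here.

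**References.** Both stopping references in 7.1.8 (2 of 2) cite 3.4.4, which holds 0 liver or QTc thresholds. The section's other references, to 7.1.6 for reporting, are correct.

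**Precedence.** No other document settles the matter. The memo of 18 September 2020 touches ECGs only as to timing. The memo of 5 January 2021 concerns screening laboratory tests. The administrative letter of 25 January 2021 adds CRP and IL-6. The SAP gives no rule on which section prevails.

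**The case against.** The best reply is that the sections do not contradict each other. Section 3.4.1 never tells a site to continue drug, so a site that stops under 7.1.8 satisfies both, and a specific rule for a named event is ordinarily read as governing that event. The gap in strength is also smaller than it first looks: 7.1.8 says *should*, whereas 3.4.1 uses *must* for its rule on stopping when continuing is against the subject's best interests. The liver example is narrow, because fever and fatigue are among the listed symptoms and are likely in patients hospitalised with COVID-19. Other safeguards exist: both events go to the sponsor within 24 hours, in the sentence next to the stopping instruction; the DMC reviews safety; treatment lasts at most 14 days; and the only scheduled on-treatment ECG is on Day 7.

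Most of this stands, and it limits how serious the point is. It does not remove it. The protocol never says that the stricter section prevails. The QTc conflict needs no unusual subject. In the liver case a listed symptom raises the 3.4.1 score to 1 of 4 but leaves its instruction at consider. Reporting does not itself stop dosing, and the best-interests rule rests on the investigator's judgement, whereas 7.1.8 sets fixed criteria.

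**Conclusion.** The point holds. For QTc the two sections share one threshold and differ in the action. For liver injury they differ in both trigger and action, and only 3.4.1 has an alternative-cause exception. Both stopping references in 7.1.8 lead to a section without the criteria.

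It should be corrected, but it does not threaten the trial's conclusions. The documents give no basis for estimating how many subjects would meet these criteria. The subjects used in the check are constructed to show how the rules diverge and carry no estimate of frequency. The conclusion rests on the current version 3.0 text and on reading the 3.4.1 QTcF values as the criteria that 7.1.8 intends, since the protocol contains no other on-treatment QTc stopping threshold.

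**What to change.** By clarification memo or amendment:

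1. Change both stopping references in 7.1.8 from Section 3.4.4 to Section 3.4.1.
2. State in 3.4.1 that study drug is discontinued when the 7.1.8 Hy's Law criteria or the confirmed QTcF criteria are met.
3. Leave the remaining 3.4.1 liver triggers as prompts to consider stopping.
4. Ask the sponsor's safety physicians to confirm whether the alternative-cause exception is meant to apply to the Hy's Law rule. Section 7.1.8 has no such exception at present, and items 1 to 3 need not wait for the answer.

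The cost is wording only, with no added procedures or data. Sections 3.4.2 and 6.6.1 ask that subjects who stop drug be kept in the study, so a firmer stopping rule need not cost endpoint data.

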7.2 Pregnancy

7.2.1 Teratogenicity

If a woman becomes pregnant when on study drug, study drug should be permanently discontinued. The investigator must counsel the subject and discuss the risks of continuing with the pregnancy and the possible effects on the fetus. Monitoring of the subject should continue until the outcome of the pregnancy is known. In the event of pregnancy in the partner of a study subject, the Investigator should make every reasonable attempt to obtain the woman's consent for release of protected health information.

7.2.2 Reporting of pregnancy

Irrespective of the treatment received by the subject, any pregnancy occurring during study drug administration or until follow-up, must be reported within 24 hours of the investigator's knowledge of the event to [REDACTED] using the Exposure in Utero form. The Investigator must make every effort to follow the pregnant partner of a male subject through resolution of the pregnancy (delivery or termination) and to report the resolution on the SAE form.

8 STATISTICAL METHODOLOGY AND ANALYSES

8.1 Statistical analysis plan

A statistical analysis plan (SAP) will be generated and approved prior to database snapshot for the interim analysis (IA). The SAP will detail the implementation of all planned statistical analysis. Any deviations from the planned analysis will be described and justified in the final clinical study report.

All safety and statistical programming will be conducted using SAS 9.4 for Windows or newer (SAS Institute Inc., Cary, NC, USA), and other statistical programming/sample size calculation software as necessary.

8.1.1 Determination of sample size

The primary efficacy endpoint of this study is the proportion of subjects who progress to death or respiratory failure by the end of study (Day 28). It is estimated that approximately 30% of enrolled subjects receiving SOC plus placebo will attain this endpoint. It is assumed that losmapimod will improve the primary endpoint by 40% over placebo. On the basis of these assumptions, a total of up to 410 subjects randomized to the losmapimod arm or the placebo arm in a 1:1 ratio (205 subjects in the losmapimod arm and 205 subjects in the placebo arm) will yield approximately 80% power in a 1-sided test at the 2.5% significance level. The sample size estimate assumes an IA will be conducted after approximately 206 subjects (103 in the losmapimod arm, and 103 in the placebo arm) have completed the Day 28 visit, to assess early futility, using the rules specified in [Section 8.9](#).

8.1.2 Analysis methods

In general, all study endpoints will be summarized using descriptive statistics. Descriptive statistics for continuous data will include number of subjects (n), mean, standard deviation, median, minimum, and maximum. Descriptive statistics for categorical data will include frequency and percentage.

Where appropriate, descriptive statistics may be presented with 95% CI.

8.1.3 Analysis sets

Full Analysis Set (FAS): The FAS will consist of all subjects who are randomly assigned to receive double-blind study drug. All analyses using the FAS will group subjects according to randomized treatment. The primary endpoint, clinical outcomes/status, survival, and pharmacodynamic endpoints will be analyzed using the FAS.

Per Protocol Set (PPS): The PPS will consist of all FAS subjects who fulfill all inclusion/exclusion criteria and do not have any significant protocol deviations. All analyses using the PPS will group subjects according to randomized treatment.

Safety Analysis Set: The safety analysis set is defined as all subjects who are randomized and receive study drug. All analyses using the Safety Analysis Set will group subjects according to treatment actually received. The safety analysis set will be used for all safety and tolerability analyses.

8.2 Protocol violations/deviations

Protocol deviations will be identified based on conditions related to the categories below:

- Protocol entry criteria
- Forbidden concomitant medications
- Missing evaluations for relevant endpoints

Fulcrum Therapeutics
Protocol FIS-001-2020

Losmapimod

- Other protocol deviations occurring during study conduct.
Major protocol deviations will be identified before study closure and listed where appropriate.

8.3 Missing, unused and spurious data

All missing or incomplete safety and PD data, including dates and times, are treated as such. Missing test results or assessments will not be imputed, and as such, are assumed missing-completely-at-random (MCAR).

For laboratory data, values below the limit of quantitation (recorded as “< LLQ”) will be set to half that limit.

Censoring rules for time-to-event endpoints will be discussed in the SAP. Imputation rules for the primary endpoint will be discussed in the SAP. The handling of any missing, unused, and spurious data will be documented in the SAP or the clinical study report.

8.4 Subject disposition

Subject disposition will be listed by subject.

The following subject data will be summarized:

- number and percentage of subjects screened,
- number and percentage of subjects enrolled,
- number and percentage of subjects completed,
- number and percentage of subjects included in safety population

A subject who completed the study is defined as a subject where the last PD assessment was completed.

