Note: All screening assessments are to be performed before dosing. If procedures required at any time point have already been performed as part of routine clinical care, these assessments do not need to be repeated, and information will be collected and entered on the eCRF from the subject's medical records. Unscheduled visits can take place at any time at the discretion of the site to check for new AEs/SAEs or to repeat key missed assessments or for other reasons.

¹ The order of assessments can be performed at the discretion of the investigator once informed consent is obtained.

² COVID-19 diagnosis to be confirmed by local testing (PCR) before randomization and first dosing. Saliva, swab, or sputum testing may be used based on local standard of care.

[figure not shown]
³ To be performed while hospitalized based on standard-of-care local assessment. Evidence of pulmonary involvement consistent with COVID-19 may also be obtained from clinical examination, per the judgment of the investigator. Evidence of pulmonary involvement obtained by clinical examination should be documented in the eCRF.

⁴ PK assessments will be performed as a ~~substudy~~ in all sentinel subjects. For those subjects requiring dialysis, a single pre- and post-dialysis PK should be obtained for review by the DMC to decide if dose adjustment is needed. PK should be measured weekly for 2 weeks at ~~week~~ (4-5 hours post dose) for subjects with renal insufficiency when possible.

⁵ Assessments for biomarkers post randomization have a window of ± 2 days. Biomarker samples to be collected in all subjects at the specified time points when possible.

⁶ Assessments for clinical/respiratory status, progression, and safety serum chemistry and hematology tests to be performed and samples to be collected while hospitalized based on standard-of-care local laboratory assessments and after discharge from the hospital by home visit or outpatient clinic visit or telemedicine call. For subjects who are discharged to home or other outpatient setting after initial hospitalization, the assessments and laboratory samples can be obtained less often but not less than at least once weekly. CRP result required to determine eligibility are based on local laboratory results at screening.

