3.3 Subject Data and Study Conduct

3.3.1 Subject Disposition

Subject disposition will be listed by subject.

The number and percentage of subjects in each of the following categories will be presented by the treatment group and overall for all screened subjects:

- screened,
- randomized,
- treated,
- randomized but not treated,
- completed the Treatment Period, and
- completed the study.

Primary reasons for discontinuation of study treatment and primary reasons for discontinued study will be tabulated.

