3.4.2 Secondary Efficacy Endpoints

Clinical status at Day 7 and Day 14:

Change in clinical status between baseline and at Days 7 and 14 will be modeled using ordinal logistic regression models, adjusting for stratification factors, sex and baseline CRP. If the subject progresses to death and the value of WHO 9-point scale is missing, the missing value of WHO 9-point will be imputed as (8) death.

Percentages for each category of the ranking scale will be tabulated by treatment arm, along with differences between treatment arms at each time point. The proportion of subjects for each of the items in the scale will be compared using an adjusted risk difference obtained from an ordinal logistic regression model, adjusting for stratification factors, sex and baseline CRP.

Total number of study days by Day 28:

(a) Free of oxygen supplementation; (b) in ICU; (c) of hospitalization; (d) free of respiratory failure; (e) alive; For each endpoint (a) – (e), a Poisson regression model will be used to assess

the relationship with treatment, adjusting for stratification factors, sex, baseline CRP and number of days on study. The key study endpoint of “oxygen free days by Day 28” will be tested at 1-sided significance level of 0.025 as outlined in Section 3.1.5.

If a patient died, the number of days of (a)-(e) are considered as having the events on and after the patient died. For example, if a patient died on Day 6. The days from Day 6 and after are considered not free of oxygen supplementation, hospitalization, ICU, and respiratory failure.

Percentage of subjects discharged from the hospital by Day 28:

Percentages of subjects discharged from the hospital will be tabulated by treatment arm, along with differences between treatment arms. The proportion of subjects will be compared using an adjusted risk difference obtained from a logistic regression model, adjusting for stratification factors, sex, and baseline CRP.

The percentage of subjects discharged from the hospital is defined as the number of subjects discharged from the hospital divided by the sum of the number of subjects who completed the study and the number of subjects who died during the study period.

A sensitivity analysis will be performed by excluding the subjects who died after being discharged from the hospital from the numerator of the above percentage calculation.

Missing data will be imputed similarly as primary endpoint for the above endpoints.

All-cause mortality at Day 28:

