Percentages of subjects will be tabulated by treatment arm, along with differences between treatment arms, at each time point. The proportion of subjects will be compared using an adjusted risk difference obtained from a logistic regression model, adjusting for stratification factors, sex, and baseline CRP.

Standard survival analysis methods will be used as sensitivity analyses to compare the time to each of these clinical events of interest (death and respiratory failure) as well as the composite thereof. Specifically, the cumulative incidence rates between two groups at Day 28 will be compared, accounting for potential differential follow-up.

Incidence of AEs/SAEs by Day 28: will be summarized by system organ class and preferred term and by treatment arm using percentages.

Incidence of AEs/SAEs is calculated by the number of subjects who developed AEs/SAEs during the study divided by the sum of the number of subjects who completed the study and the number of subjects who died during the study period. (see above edit)

Incidence of clinically significant changes by Day 28: Percentage of subjects with clinically significant changes in laboratory parameters, ECG, and vital sign measurements will be computed for each treatment arm along with associated 2-sided 95% Clopper-Pearson CI.

Changes in the assessments will be considered as clinically significant if the Baseline assessment is not clinically significantly abnormal and there has been at least one occurrence of post-Baseline assessments with a clinically significant abnormal result by Day 28.

[figure not shown]
Death is not considered a form of missing data or censoring. The incidence of clinically significant changes is calculated by the number of subjects with clinically significant changes during the study divided by the sum of the number of subjects who completed the study and the number of subjects who died during the study period.

Clearance of quantifiable viral RNA by Day 7: percentages of subjects with clearance of quantifiable viral RNA will be tabulated by treatment arm, along with differences between treatment arms, at each time point. The proportion of subjects will be compared using an adjusted risk difference obtained from a logistic regression model, adjusting for stratification factors, sex, and baseline CRP.

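### Protocol 8.4 ties study completion to the last PD assessment, not to Day 28 status, and the SAP builds three secondary denominators on it

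*Protocol*

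**What the plan says.** Protocol 8.4 (Subject disposition) gives the only definition of a completer in either document: "A subject who completed the study is defined as a subject where the last PD assessment was completed". It mentions neither the Day 28 visit nor survival nor respiratory status.

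SAP 3.3.1 lists "completed the study" as a disposition category and does not define it. SAP section 6 lists two changes from the protocol, the FAS definition and the handling of covariates. Completion is not among them, so the protocol definition stands.

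SAP 3.4.2 then uses completion as a denominator three times:
- Discharge by Day 28: the number discharged "divided by the sum of the number of subjects who completed the study and the number of subjects who died during the study period".
- Adverse events: "Incidence of AEs/SAEs is calculated by the number of subjects who developed AEs/SAEs during the study divided by the sum" of completers and deaths.
- Safety changes: "The incidence of clinically significant changes is calculated by the number of subjects with clinically significant changes during the study", over the "sum of the number of subjects who completed the study and the number of subjects who died during the study period".

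Other SAP text points elsewhere. SAP 3.2.1 assigns clinical outcome and status endpoints to the FAS. SAP 3.2.2 assigns all safety analyses to the Safety Analysis Set, and the TEAE overview in 3.5.1 uses that set. SAP 3.4.2 itself says that missing discharge data are imputed as for the primary endpoint, and that all three of these endpoints are analysed in a similar way to the primary.

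**The concern.** A PD sample and a known outcome are different things. Protocol 6.3.1 records discharge details and end-of-study survival independently of any sampling, and the footnotes to Protocol Table 1 allow status after discharge to be obtained by telemedicine. The schedule attached to the Administrative Letter of 25 January 2021 foresees gaps in sampling: "Biomarker samples to be collected in all subjects at the specified time points when possible". A subject known to be alive and free of respiratory failure at Day 28 can therefore be a non-completer because of one missed sample.

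Two things are at stake. First, the reported completion rate would not show how many subjects have a known primary outcome. Second, three secondary or safety percentages would depend on PD sampling. Deaths always stay in the denominator while some survivors leave it, and the distortion differs between arms if sampling does.

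**Working it through.** **What the plan offers to check.** No completion rate or missing-sample rate is stated, so there is no plan figure to reproduce on this point. The only plan input used below is N = 410 (Protocol 8.1.1).

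**Does the rule reach the primary analysis?** SAP 3.1.8, 3.2.1 and 3.4.1 analyse the primary endpoint in the FAS with multiple imputation of unknown status. Completion does not enter. The stated boundaries (-0.67873 at 103 per arm, -1.91358 at 205 per arm) give type I error 0.0250 and power 79.4% to 80.2% (pooled or unpooled variance) for 0.18 against 0.30. That agrees with the stated 0.025 and 80%, and nothing in the calculation involves completion. None of the three affected percentages is in the testing sequence of SAP 3.1.5.

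**Illustration (assumed rates).** Of 410 subjects, all with known Day 28 status:
- discharged alive 80% = 328
- still in hospital 10% = 41
- dead 10% = 41

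SAP denominator = PD-defined completers + deaths = 410 − survivors who missed the last PD sample.

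*Misses only among discharged subjects, numerator restricted to the same subjects:*
- 10% missed: 32.8 leave. (328 − 32.8)/(410 − 32.8) = 295.2/377.2 = 78.3%
- 20% missed: 65.6 leave. (328 − 65.6)/(410 − 65.6) = 262.4/344.4 = 76.2%

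The true value is 328/410 = 80%. Two arms with identical outcomes but 10% and 20% missed samples would differ by 78.3 − 76.2 = 2.1 points.

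*Misses spread evenly over all 369 survivors (328 + 41):*
- 10% missed: 295.2/(410 − 36.9) = 295.2/373.1 = 79.1%
- 20% missed: 262.4/(410 − 73.8) = 262.4/336.2 = 78.0%

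The shift is smaller but not zero, because deaths are always retained.

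*Completion count, misses among discharged subjects only:* 369/410 = 90.0% are alive with known status. The PD rule reports (369 − 32.8)/410 = 82.0% or (369 − 65.6)/410 = 74.0%.

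**Which assessment is last?** The biomarker row of Table 1 is not visible. The visible viral sample for all subjects is on Day 1 and on Day 7, or earlier if discharge comes first. SAP 3.2.3 limits the PK/PD set to sentinel subjects, while 3.2.1 places PD endpoints in the FAS. For the roughly 400 non-sentinel subjects, the sample that decides completion is therefore not identified.

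**The case against.** The strongest reply is that other SAP text already limits the damage. Discharge data are to be imputed as for the primary, the three endpoints are analysed in a similar way to it, and safety analyses belong to the Safety Analysis Set. A programmer could follow that text and never use completers in a treatment comparison. This stands in part: bias in the model-based comparisons is not established. It does not remove the point, because the percentages themselves are explicitly defined on completers plus deaths, and the conflict leaves the choice of denominator open until data are in hand.

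A second reply is that samples after discharge are planned for. Protocol 3.1 provides for local laboratories and home blood draws, and footnote 14 of Table 1 provides for outpatient laboratory work. This also stands. A reader might infer that telemedicine follow-up means no sample, but the documents do not say so. That missed draws concentrate in discharged subjects is plausible and unsupported by any figure.

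Two stronger readings are tempting:
- A reader might infer that subjects lost after their last PD sample count as completers. That has practical effect only if the last PD assessment precedes Day 28, which cannot be confirmed while the biomarker row is not visible.
- A reader might take the unrestricted numerators of SAP 3.4.2 and obtain 328/377.2 = 87.0% or 328/344.4 = 95.2% in the illustration. Those figures come from mismatched numerators and denominators, which is a separate defect. They also point in the opposite direction from the effect of the completion rule itself.

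**Conclusion.** The point holds within limits. The completion rule in Protocol 8.4 is wrong for the use the SAP makes of it: it can remove subjects with a known Day 28 status from three secondary or safety percentages and from the completion count. The SAP also contradicts itself on which denominator applies.

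The size rests on assumed rates. With 10% to 20% of discharged subjects missing the sample and matched numerators, a true 80% discharge rate is reported as 78% to 76%. If misses are unrelated to discharge among survivors, it is 79% to 78%. The completion count moves more, from 90% to 82% or 74% under the first assumption. The primary result, the testing sequence, alpha and power do not change. The correction is worth making before the final analysis because it is cheap and settles a choice that should not be made after the data are seen.

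**What to change.** 1. In Protocol 8.4 and SAP 3.3.1, replace the definition with: *A subject completed the study if alive at Day 28 with survival and respiratory-failure status through Day 28 recorded by any contact method, regardless of missed PD samples; deaths are tabulated separately.* Report PD sample completeness as its own line.
2. In SAP 3.4.2, replace the completers-plus-deaths denominators. Use the FAS for discharge by Day 28, with the imputation already stated there, and the Safety Analysis Set for AE/SAE incidence and clinically significant changes.

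The words requiring the subject to be alive matter. If a recorded death also counted as completion and a completers-plus-deaths denominator survived anywhere, each death would enter twice: 328/(410 + 41) = 328/451 = 72.7% against a true 80%. Step 2 is also needed alongside step 1. Otherwise subjects truly lost to follow-up still leave the denominator, and the conflict with SAP 3.2.1 and 3.2.2 remains.

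The cost is one sentence of definition and three denominator statements. If the protocol is not amended, the SAP can carry the definition with an entry in section 6. No new data are required, and sample size, alpha and power are unchanged.
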